Second, although ESHAP is very active in low-grade NHL, it is not often utilized by community oncologists as a salvage regimen. Therefore, most pretreated patients have not seen these agents and therefore their lymphomas should be responsive to ESHAP. After treatment with two cycles of preparative ESHAP most patients should have minimal residual disease and therefore have higher response to Zevalin. It is our hypothesis that tumor mass reduction with standard chemotherapy in relapsed follicular lymphoma will result in a significant prolongation of time to progression following Zevalin therapy, changing the natural history of relapsed disease.

The TTP and OS results of this study will be compared with reported outcomes in published trials of Zevalin alone to assess whether there is sufficient improvement to merit further study of this approach in this setting. We have designed the trial to detect an increase in 1-year PFS from a historical value of 50% to 67.3%, which corresponds to an increase in median TTP from 12 months to 21 months.

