- d. Toxicity Assessment: Adverse events are to be recorded on an ongoing basis and on appropriate source documents at the clinical site and in the patient's case report form.

5.E Follow-Up Evaluations

5.E.1 Short-Term Follow-Up Period

- a. The following tests/evaluations will be obtained at 6-month intervals (+/- 7 days) for a period of 2 years (24 months) following the Zevalin:
 - History & Physical examination, including vital signs (BP, temperature & pulse), height, weight, Body Surface Area (BSA), and performance status (Appendix B).
 - Laboratory tests including:
 - o Complete blood count (CBC) with differential and platelet count
 - o Serum chemistries BUN, creatinine
 - o LDH
 - Disease Assessment (Only required at 6-month intervals for a period of 2 years (24 months) following Zevalin):
 - o Total of all measurable indicator lesions.
 - CT or PET scan of the chest, abdomen and pelvis (Restaging of disease by CT scan is recommended every 6 months up to Month 24, then annually until year 5).

5.E.2 Long-Term Follow-Up Period

- a. The following tests/evaluations will be obtained annually (+/- 30 days) for an additional 3 years after the completion of the Short-Term Follow-Up period:
 - History & Physical examination, including vital signs (BP, temperature & pulse), height, weight, Body Surface Area (BSA), and performance status (Appendix B).
 - Laboratory tests including:
 - o Complete blood count (CBC) with differential and platelet count
 - o Serum chemistries BUN, creatinine
 - LDH
 - Disease Assessment:
 - o Total of all measurable indicator lesions.
 - o CT or PET scan of the chest, abdomen and pelvis

Once the patients have completed the Short-Term Follow-Up period they will continue to be followed for 3 years on an annual basis (+/- 30 days) for survival and disease status. Patients should be followed by physical exam and, if clinically indicated by Good Medical Practice, CT or PET scans. Patients will be followed for 3 years or until patient starts alternate treatment or is removed from study to allow determination of study endpoints.

5.F Disease Progression Evaluations/Off-Study

Patients who develop disease progression during the treatment period and who do not begin other anti-cancer therapy will continue to be followed for routine safety and efficacy for a total of 30 days following any discontinuation of treatment for any cause.

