11 REMOVAL OF PATIENTS FROM THIS STUDY

11.A Criteria for Discontinuation of a Patient's Study Participation

The date of discontinuation and reason(s) for patient discontinuation from the study will be recorded in the CRF. All evaluations which are required at the final study visit must by conducted for each patient who discontinues treatment, regardless of the reason (see Section 5.F.1).

- Disease Progression: Patients will be taken off study if they have progressive disease (PD) or clinically significant deterioration at any time during the study.
- Personal Reasons: Patients may choose to withdraw from the study at any time.
- Clinical Judgment of the Investigator: A patient may be withdrawn from the study, if in the opinion of the investigator, it is not in the patient's best interest to continue.
- Requiring other anti-neoplastic therapies

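### Section 1.E uses overall survival to judge merit, but the off-study rules would censor survival at progression or new therapy, and conflicting follow-up text is unreconciled

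*Combined protocol and SAP*

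**What the plan says.** Section 1.E: "The TTP and OS results of this study will be compared with reported outcomes in published trials of Zevalin alone". The purpose given is "to assess whether there is sufficient improvement to merit further study of this approach in this setting". Appendix D (Table 2) defines OS in all patients, from trial entry, with death of any cause as the event.

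Three rules limit how long patients are observed:
- **11.A:** "Patients will be taken off study if they have progressive disease (PD) or clinically significant deterioration at any time during the study". Another listed ground for removal is "Requiring other anti-neoplastic therapies".
- **5.E.2, repeated in an Appendix A footnote:** the annual contacts are for survival and disease status, but "Patients will be followed for 3 years or until patient starts alternate treatment or is removed from study to allow determination of study endpoints".
- **5.F:** patients who progress during the treatment period and start no other anti-cancer therapy "will continue to be followed for routine safety and efficacy for a total of 30 days following any discontinuation of treatment".

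Other text points the other way:
- **3.A** follows patients for progression and survival after they stop treatment, but only those with more than 25% residual marrow involvement after ESHAP.
- **3.B** gives five years of follow-up after treatment, without qualification.
- **13.C** lists death among the occasions for submitting forms.

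Section 2 has no OS objective. Section 12.C tests 1-year PFS, and the Kaplan-Meier analysis in Section 12 is for time to progression only.

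**The concern.** If survival is observed only until progression or new therapy, OS is censored at the moment the risk of death is likely to rise. That censoring is informative. Kaplan-Meier treats the patients who leave as having the same later risk as those who remain progression-free, so the curve sits too high. Published OS for Zevalin alone, if it includes deaths after progression, would be compared with a curve that largely leaves them out. The error favours ESHAP-Zevalin, and a single-arm trial has no concurrent control to expose it.

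**Working it through.** **1. The plan's own figures.** Inputs from Section 12: 1-year PFS 50% against 67.3%, one-sided alpha 0.10, power 90%.

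n = [(1.2816·√(0.5·0.5) + 1.2816·√(0.673·0.327)) / 0.173]² = 51.54, rounded up to 52. This reproduces the stated sample size. Exponential medians are 12·ln2/(−ln 0.5) = 12.0 months and 12·ln2/(−ln 0.673) = 21.0 months, also as stated. OS enters neither calculation.

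**2. Share with a progression event.** 1 − 0.5^(t/median):

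| Time | Median 12 months | Median 21 months |
|---|---|---|
| 24 months | 75% (39 of 52) | 55% (28 of 52) |
| 60 months | 97% (50 of 52) | 86% (45 of 52) |

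These are upper bounds on the share censored for OS because of progression. The medians are derived from PFS, and Appendix D counts death from NHL as a PFS event, so some of these events would be observed deaths.

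**3. What happens to these patients.** 11.A takes them off study, and 5.E.2 ends follow-up on removal. 5.F.1 and the off-study column of Appendix A schedule one set of tests within 4 weeks and no later contact. Section 9 does not close the gap: serious events after other anti-cancer therapy need not be reported unless they fall within 30 days of the infusion, are thought to be drug-related, or are a new malignancy.

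**4. Size of the bias, under assumptions.** The documents give no death rates. Assumed: death before progression d = 1, 2 or 4% per year; median survival after progression 3, 5 or 8 years; constant hazards. Let λ be the yearly PFS hazard (ln2 divided by the median in years) and μ the yearly death hazard after progression.

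- True OS: S(t) = e^(−λt) + (λ−d)·[e^(−μt) − e^(−λt)]/(λ−μ).
- Kaplan-Meier OS censored at progression tends to e^(−dt).

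Example: TTP median 12 months (λ = 0.693), d = 0.01, post-progression median 3 years (μ = 0.231), t = 5 years. True OS = 0.031 + (0.683/0.462)·(0.315 − 0.031) = 0.45. Censored curve = e^(−0.05) = 0.95.

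Four of the 18 scenarios simulated, including the extremes of the gap. Deaths seen include those within 30 days after progression, granted to every patient, which is more generous than 5.F:

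| TTP median | d | Post-progression median | True 5-year OS | Censored curve | Deaths in 52 by 5 years | Deaths seen |
|---|---|---|---|---|---|---|
| 12 mo | 1% | 3 y | 45% | 95% | 28.6 | 1.7 (6%) |
| 12 mo | 4% | 3 y | 43% | 82% | 29.6 | 3.8 (13%) |
| 21 mo | 1% | 8 y | 78% | 95% | 11.7 | 1.4 (12%) |
| 21 mo | 4% | 8 y | 73% | 82% | 14.2 | 4.8 (34%) |

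Over all 18 scenarios, true 5-year OS is 43-78%, the censored curve shows 82-95%, and 66-94% of deaths are missed. Within a scenario the overstatement runs from 9 points (82 − 73) to 50 points (95 − 45).

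**5. Sensitivity to the 30-day window.** The censored curve above stops at progression itself. If every patient were also kept at risk for w = 30/365.25 = 0.082 years afterwards, the average hazard in the risk set is about [d + μ(λ−d)w]/[1 + (λ−d)w]. For the example this is (0.010 + 0.231·0.056)/1.056 = 0.0217 per year, giving e^(−0.109) = 0.90 against a true 0.45. The bias shrinks slightly and remains large.

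**The case against.** The strongest reply is that OS in 1.E is one sentence of rationale. The next sentence of 1.E sizes the trial on 1-year PFS, 12.C accepts or rejects on 1-year PFS alone, and Section 2 omits OS. The background quotes no OS figure for Zevalin alone, so there is not even a stated benchmark. All of this stands. A reader might infer from 1.E that the go/no-go decision rests on OS; the documents do not support that.

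A reader might also infer that deaths after progression will certainly go unrecorded. That is too strong. 13.C expects a form at death, 3.B promises five years, and 5.E.2 itself names survival as a purpose of follow-up. These passages show some intent to capture survival. They do not override the explicit end-points in 11.A and 5.E.2, and 3.A's survival follow-up covers one subgroup. The result is a conflict that sites could resolve differently.

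5.F should not be read as a general 30-day limit, because it covers only progression during the treatment period without new therapy.

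Finally, the plan's medians alone do not show that most deaths are missed. They give the share with a progression event, which is a different quantity. The statement about deaths needs the assumed rates in the working, although it held in all 18 scenarios tried.

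**Conclusion.** The concern holds as an unreconciled conflict between a stated OS comparison and the follow-up rules. If 11.A and 5.E.2 are applied as written, up to 55-75% of patients leave survival observation because of progression by 24 months, and up to 86-97% by 60 months, on the plan's exponential medians. The direction of the bias is upward provided the risk of death rises after progression. Its size rests on the assumed rates: 5-year OS overstated by 9 to 50 percentage points and 66-94% of deaths missed. The primary PFS test, its error rates and N=52 do not change. What is at risk is any OS statement made beside the PFS result in support of further study.

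**What to change.** Reconcile 3.A, 3.B, 5.E.2 (with the Appendix A footnote), 5.F, 11.A and 13.C so that going off study for progression or new therapy does not end survival follow-up. Collect vital status, with date and cause of death, yearly to year 5 by chart review or telephone, for all treated patients who have not withdrawn consent. Do this at every participating site, since 12.A describes two institutions. Add to Section 12 a Kaplan-Meier OS estimate from trial entry, with censoring at the date last known alive.

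If this follow-up is not wanted, delete OS from the comparison in 1.E.

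No change to treatment or scan rules is proposed. The first option costs an amendment and a small yearly status check on about 52 patients, with no added visits or procedures. On the assumed rates it would capture about 12 to 30 deaths by year 5, against about 1 to 5 under the present off-study rules. The second option costs one edited sentence.

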2 OBJECTIVES

2.A Primary Objectives

- 2.A.1 To evaluate the 1-year progression-free survival (PFS) of patients with relapsed follicular non-Hodgkin's lymphoma (NHL) treated with ESHAP chemotherapy for cytoreduction (2 cycles) followed by Ibritumomab tiuxetan (Zevalin) radioimmunotherapy.
- 2.A.2 To evaluate the median TTP of patients with relapsed follicular NHL treated with ESHAP chemotherapy for cytoreduction (2 cycles) followed by Ibritumomab tiuxetan (Zevalin) radioimmunotherapy.

2.B Secondary Objective

2.B.1 To evaluate the overall (ORR) and complete response rates (CR) of patients with relapsed follicular NHL treated with ESHAP chemotherapy for cytoreduction (2 cycles) followed by Ibritumomab tiuxetan (Zevalin) radioimmunotherapy.

3 STUDY DESIGN

3.A Treatment Summary

After informed consent has been obtained, patients will undergo screening to assure eligibility for the study. After two cycles of ESHAP have been given, patients will be restaged to determine response. Patients with residual involvement of more than 25% of bone marrow after the two cycles of ESHAP will be taken off treatment and followed for time to progression and survival. Patients experiencing disease stabilization or reduction with less than 25% residual bone marrow involvement will undergo imaging for biodistribution. If biodistribution is acceptable, then patients will receive the Zevalin treatment and undergo a second disease evaluation for response assessment. Thereafter, patients will be followed at 6 month intervals (Short-term follow-up) for 2 years, and then annually (Long-Term follow-up) for an additional 3 years

3.B Study Duration

The estimated active accrual period for this study is 5 years. After completion of treatment, patients will be followed for 5 years to allow determination of study endpoints.

4 STUDY POPULATION

4.A Inclusion Criteria

- 4.A.1 All patients must have a history of relapsed follicular non-Hodgkin's lymphoma. Patients must be in first, second, third, or fourth relapse.
- 4.A.2 Lymphomas must express the CD20 antigen as demonstrated by either flow cytometry or immunoperoxidase staining of paraffin sections using anti-CD20 antibodies.

- 4.A.3 Patients must have bulky Stage II, Stage III, or Stage IV extent of disease by the Ann Arbor classification (see Appendix F). Bulky disease is defined as any tumor measuring 10.0 cm or greater or occupying ≥ one-third of the chest diameter.
- 4.A.4 All patients must have bidimensionally measurable disease (as defined in Appendix D) documented within 28 days prior to C1, Day 1.
- 4.A.5 Pathology Review: Adequate sections from the diagnostic specimen or core needle biopsies which are large enough to show architecture (bone marrow biopsies and fine-needle aspirates are insufficient) is desirable. At a minimum, a report documenting the diagnosis is required.
- 4.A.6 Patients must have a unilateral or bilateral bone marrow aspirate and biopsy performed within 28 days prior to Cycle 1, Day 1.
- 4.A.7 Patients must have a CT or PET scan of chest, abdomen, and pelvis within 28 days prior to Cycle 1, Day 1.
- 4.A.8 Patients must have an LDH and β-2 microglobulin within 28 days prior to Cycle 1, Day 1.
- 4.A.9 Patients must have received prior chemotherapy for lymphoma.

 (Patients must have had at least 1, but no more than 4 prior chemotherapy regimens for lymphoma. This includes investigational agents and/or other antibody therapy. All prior therapy must have been completed at least 3 weeks prior to registration. Patient who previously received rituximab must have completed this therapy 6 weeks prior to registration. If rituximab is given as a single agent after relapse, it is considered a separate regimen and will be counted as such. If the rituximab is given in combination for either the first or second relapse or as consolidation after a chemotherapy regimen without an intervening relapse, it will considered part of the combination regimen and counted as one prior therapy. Patients must have recovered from any prior-therapy-related toxicities prior to Cycle 1, Day 1.)
- 4.A.10 All patients must have a Zubrod performance status of 0, 1, or 2 (see Appendix B).
- 4.A.11 Patients must be 18 years old or older.
- 4.A.12 Patients must have absolute neutrophil count (segmented neutrophils and bands) 1,500 /μL and platelets > 100,000/μL within 28 days prior to Cycle 1, Day 1 unless decreased counts have been shown to be due to marrow involvement with NHL.

NOTE: For progression to treatment with Zevalin: Patients must have < 25% bone marrow involvement with lymphoma as determined after cycle 2 of ESHAP. For patients without bone marrow involvement, there must be adequate bone marrow reserves as defined under EXCLUSION. (These criteria must be strictly met for adequate patient safety.)

Additionally, patients must have:

- serum creatinine value < 2.0 and total bilirubin < 2.0.
- Platelet counts $\geq 150,000/\text{mm}^3$, these patients will receive a dose of 0.4 mCi/kg of Zevalin
- Platelet counts from 100,000/mm³ to 149,000/mm³, these patients will receive a 0.3 mCi/kg dose of Zevalin
- 4.A.13 Patients with renal insufficiency or renal failure (serum creatinine > 2.0 mg/dL; creatinine clearance < 50 ml/min) are not eligible for this study. A serum creatinine or creatinine clearance must be obtained within 28 days prior to Cycle 1, Day 1.
- 4.A.14 Pregnant or nursing women may not participate. Women or men of reproductive potential must agree to use an effective contraceptive method as determined by the treating physician from the time of Cycle 1, Day 1 to 6 months after receiving the Zevalin.
- 4.A.15 No prior malignancy is allowed except for adequately treated basal cell or squamous cell skin cancer, in situ cervical cancer, or other cancer for which the patient has been disease-free for 5 years.
- 4.A.16 If Day 28 falls on a weekend or holiday, the limit may be extended to the next working day. In calculating days of tests and measurements, the day a test or measurement is done is considered Day 0. Therefore, if a test is done on a Monday, the Monday 4 weeks later would be considered Day 28. This allows for efficient patient scheduling without exceeding the guidelines.
- 4.A.17 All patients must be informed of the investigational nature of this study and give written informed consent in accordance with institutional and federal guidelines.
- 4.A.18 Expected survival \geq 3 months

4.B Exclusion Criteria

- 4.B.1 Patients with impaired bone marrow reserve, as indicated by one or more of the following:
 - Platelet count < 100,000 cells/mm³
 - Hypocellular bone marrow (cellularity < 10%)
 - Marked (>_10%) reduction in bone marrow precursors of one or more cell lines (granulocytic, megakaryocytic, erythroid) (beyond that which would be expected for the patient's age and bone marrow cellularity
 - History of failed stem cell collection
- 4.B.2 Prior radioimmunotherapy

- 4.B.3 Presence of CNS lymphoma. Patients must not have clinical evidence of central nervous system (CNS) involvement by lymphoma.
- 4.B.4 Patients with abnormal liver function: total bilirubin > 2.0 mg/dL
- 4.B.5 Patients with abnormal renal function: serum creatinine > 2.0 mg/dL or creatinine clearance < 50 ml/min.
- 4.B.6 Patients who have received prior external beam radiation therapy to > 25% of active bone marrow (involved field or regional)
- 4.B.7 Patients who have received G-CSF or GM-CSF therapy within 2 weeks prior to treatment
- 4.B.8 Serious nonmalignant disease or infection which, in the opinion of the investigator and/or the sponsor, would compromise other protocol objectives
- 4.B.9 Major surgery, other than diagnostic surgery, within 4 weeks
- 4.B.10 Patients with pleural effusion

4.C Number of Patients to be Enrolled

All patients who receive at least one dose of chemotherapy ESHAP will be considered evaluable and will be included in the analysis. Fifty-two evaluable patients are needed. Although it is considered highly unlikely that a patient who has given consent (enrolled) for treatment would not be treated, if this were to occur, an additional patient would be enrolled to meet the goal of 52 evaluable patients.

4.D Patient Enrollment Procedure

All ethical, regulatory, technical, and scientific approvals must be in place before study registrations will be accepted. All patients will be registered centrally with the Clinical Research Coordinator based in the Arizona Cancer Center at [contact]. The Clinical Research Coordinator will assign each patient a sequential number. Prior to registration, the fully signed informed consent must be presented and all inclusion and exclusion criteria will be reviewed with the registering investigator or designee. All source documentation needed to confirm eligibility must be available for this review.

